3.5.7.2 Eliciting and Documenting Adverse Events

The investigator is responsible for ensuring that all AEs, SAEs and AESI are recorded in the eCRF and reported to the Sponsor. Unsolicited AEs will be assessed during the Vaccination Phase from the time of the first dose administration at Day 1 through Day 57 (±7 days). Serious AEs, MAAEs, and AESI will be assessed from Day 1 through Month 13 (EOS Visit), as specified in the Schedule of Events (Table 5). Any AEs occurring before receipt of the vaccine will be analyzed separately from TEAEs.

At every clinic visit or telephone contact, participants will be asked a standard question to elicit any medically-related changes in their well-being according to the scripts provided. Participants will also be asked if they have been hospitalized, had any accidents, used any new medications, or changed concomitant medication regimens (both prescription and over-the-counter medications).

In addition to participant observations, data from clinical laboratory test results, physical examination findings, or other documents relevant to participant safety classified as an AE will be documented on the AE page of the eCRF.

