7.6.2 Adverse Events

An unsolicited AE is any AE reported by the participant that is either (1) not specified as a solicited AE in the protocol or (2) specified as a solicited AR in the protocol, but its onset occurs outside of the protocol-defined post vaccination period for reporting solicited AEs (ie, for the 7 days after each vaccination). A solicited ARs that meet the criteria for an SAE will also be recorded as an unsolicited AE.

A treatment-emergent AE (TEAE) is defined as any AE not present before exposure to vaccine or any AE already present that worsens in intensity or frequency after exposure. Only TEAEs are collected in this study.

An MAAE is defined as an AE that leads to an unscheduled visit to a healthcare practitioner.

Unsolicited AEs will be coded by PT and SOC using MedDRA and summarized by treatment, vaccination (first or second) and overall. Summaries for each vaccination will include AEs that occur during the 28 -day follow-up period after each vaccine.

All summaries of unsolicited AEs will present number and percentage of subjects in each category. For those summaries presented by PT, the preferred terms will be sorted in descending order of frequency within the mRNA-1893 treatment group.

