7.6.2.3 TEAEs by System Organ Class and Preferred Term

The following summary tables of TEAEs will be provided by MedDRA SOC and PT using frequency counts and percentages (i.e., number and percentage of participants with an event) for all participants, for all flavivirus seropositive participants and for all flavivirus seronegative participants. When summarizing the number and percentage of participants with an event, participants with multiple occurrences of the same AE or a continuing AE will be counted once. Only the maximum severity level will be presented and an AE with missing severity will be counted as Grade 3/severe in the severity summaries. Only the strongest relationship level will be presented and an AE with missing relationship will be counted as related in the relationship summaries.

- All unsolicited TEAEs
- All unsolicited treatment-related TEAEs
- All unsolicited TEAEs through 7 days after any vaccination
- All unsolicited treatment-related TEAEs through 7 days after any vaccination
- All unsolicited TEAEs of Grade 3 or higher through 7 days after any vaccination
- All unsolicited treatment-related TEAEs of Grade 3 or higher through 7 days after any vaccination
- All unsolicited TEAEs of Grade 2 or higher through 7 days after any vaccination
- All unsolicited treatment-related TEAEs of Grade 2 or higher through 7 days after any vaccination
- All unsolicited TEAEs of Grade 3 or higher through 28 days after any vaccination
- All unsolicited treatment-related TEAEs of Grade 3 or higher through 28 days after any vaccination
- All unsolicited TEAEs of Grade 2 or higher through 28 days after any vaccination
- All unsolicited treatment-related TEAEs of Grade 2 or higher through 28 days after any vaccination

- All unsolicited TEAEs within 60 minutes after any vaccination
- All unsolicited treatment-related TEAEs within 60 minutes after any vaccination
- All unsolicited serious TEAEs after any vaccination
- All unsolicited serious treatment-related TEAEs after any vaccination
- All unsolicited TEAEs of special interest after any vaccination
- All unsolicited treatment-related TEAEs of special interest after any vaccination

7.6.3 **Clinical Laboratory Evaluations**

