10.4 Appendix D: Imputation Rules for Missing AE dates

Imputation rules for missing or partial AE start/stop dates are defined below:

- 1. Missing or partial AE start date:
 - a. If only DAY is missing, use the first Day of the month, unless:
 - i. The AE end date is after the date of first vaccination or is missing AND the start Month and year of the AE coincide with the start Month and year of the first vaccination. In this case, use the date of first vaccination

^[1] includes medications with completely missing start date

^[2] includes medications with completely missing end date

Protocol mRNA-1893-P101

- b. If DAY and Month are both missing, use the first Day of the year, unless:
 - i. The AE end date is after the date of first vaccination or is missing AND the start year of the AE coincides with the start year of the first vaccination. In this case, use the date of first vaccination
- c. If DAY, Month and Year are all missing, the date will not be imputed. However, if the AE end date is prior to the date of first vaccination, then the AE will be considered a pre-treatment AE. Otherwise, the AE will be considered treatment-emergent.
- 2. Missing or partial AE end dates will not be imputed

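### SAP Appendix D dates a partially dated AE before dose 1 if it ended on the day of dose 1, and has no rule for some partial end dates

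*SAP*

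**What the plan says.** SAP Appendix D (10.4) governs incomplete AE dates.

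- **Rule 1.a, day missing.** The default is "If only DAY is missing, use the first Day of the month, unless" rule 1.a.i applies. That exception assigns the dose-1 date, and its condition is "The AE end date is after the date of first vaccination or is missing AND the start Month and year of the AE coincide" with those of dose 1.
- **Rule 1.b, day and month missing.** The default is the first day of the year. Exception 1.b.i applies the same test at year level: "The AE end date is after the date of first vaccination or is missing AND the start year of the AE coincides" with that of dose 1.
- **Rule 1.c, start wholly unknown.** No date is imputed and only a status is assigned: "if the AE end date is prior to the date of first vaccination, then the AE will be considered a pre-treatment AE". Every other such AE is treatment-emergent.
- **Rule 2, end dates.** "Missing or partial AE end dates will not be imputed".

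SAP 7.1 starts the 28-day reporting timeframe at a vaccination, and SAP 7.6.2 uses that follow-up period for the per-vaccination AE summaries. Appendix A gives [1,29] as the time frame after the first vaccination. On collection, SAP 7.6.2 states "Only TEAEs are collected in this study", and Protocol 3.5.7.2 states "Unsolicited AEs will be assessed during the Vaccination Phase from the time of the first dose administration at Day 1".

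**The concern.** The exception is there to stop an AE that could have followed dose 1 from being given a pre-dose date merely because its onset day was not recorded. As worded, it misses one boundary case. An AE that ended on the dose-1 date has an end date that is neither later than that date nor missing, so the default applies and the start moves back to the first of the month or year.

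A second gap is one of silence. Rule 2 names missing and partial end dates as two things and imputes neither. Rules 1.a.i and 1.b.i mention only missing ones. Where a partial end date could lie on either side of dose 1, the SAP does not say which branch applies, so two programmers following it could reach different counts.

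At stake is the second primary endpoint in SAP 4.1, unsolicited AEs in the 28 days after each vaccination. An AE given a start before Study Day 1 is not in that period.

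**Working it through.** The plan states no figure on this point, so there is none to reproduce. The check applies the rules as written to illustrative dates.

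**Inputs.** The Appendix D rules above. Study Day from SAP 7.1: date − dose-1 date if before dose 1, and date − dose-1 date + 1 otherwise. Window [1,29] from Appendix A. Group sizes from SAP Table 1: 24 vaccinated per dose level, 20 seronegative and 4 seropositive.

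**Case A: start day missing, start month matches dose 1, complete end date equal to the dose-1 date.** The end date is not later than dose 1 and not missing, so the default applies.

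| Dose 1 | Imputed start | Study Day | In [1,29]? |
|---|---|---|---|
| 1 Sep | 1 Sep | 1 − 1 + 1 = 1 | yes |
| 2 Sep | 1 Sep | 1 − 2 = −1 | no |
| 17 Sep | 1 Sep | 1 − 17 = −16 | no |
| 30 Sep | 1 Sep | 1 − 30 = −29 | no |

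If the month is missing too, the start becomes 1 January. In 2019, 1 September is day 244 of the year and 30 September is day 273. The Study Days are then 1 − 244 = −243 and 1 − 273 = −272, both outside.

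*Comparison.* If the end date is one day later, or is missing, the exception applies and the AE is dated to Study Day 1 in every row.

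**Rule 1.c set beside it.** Take the same end date with no start date at all. The end date is not before dose 1, so the AE is treatment-emergent. Rule 1.c puts the dose-1 date on the post-dose side of the line; rules 1.a.i and 1.b.i put it on the other. SAP 7.1 calls the vaccination date Study Day 1, and Table 4 in Appendix C groups a medication stopped on that date with later stops. Both agree with rule 1.c.

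**Case B: partial end date, dose 1 on 17 September.**

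- End in October, day unknown: the earliest possible date is 1 October, which is after 17 September. The exception applies and the AE is kept at Study Day 1.
- End in September, day unknown: the possible dates, 1 to 30 September, span dose 1. Treated as missing, the AE is at Study Day 1. Treated as neither missing nor shown to be later, it is at Study Day −16. The text does not choose.

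Appendix C avoids this for medications by imputing partial stop dates to the last day of the month or year. Appendix D has no equivalent.

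**Scale.** A participant whose only AE in a table row is lost lowers that row by 1/24 = 4.2 points in a dose group. Within its serostatus subgroups the figures are 1/20 = 5.0 points (seronegative) and 1/4 = 25 points (seropositive).

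**After the change.** With *on or after*, every Case A row gives Study Day 1. With a partial end date treated as missing unless clearly before dose 1, the September example also gives Study Day 1.

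**The case against.** The strongest reply is that such records should be rare. Participants are observed for 60 minutes after each dose, telephoned on the next two days and asked to keep a daily diary. Onset time is a collected AE field, and data entry is due within 3 business days. Case A needs a known end date on the day of dose 1 together with an unknown start day, which is an unusual record. This stands and limits the size of the point. It does not remove it: Protocol 3.5.2 requires reactions first reported verbally at a visit to be entered as unsolicited AEs, and those rest on recall.

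A second reply is that rule 1.c assigns a status while rules 1.a and 1.b assign a date. This also stands. An AE with no start date cannot be placed in [1,29] either, so the contrast shows only that Appendix D draws the dose-1 line in two places. It does not show that a wholly undated AE fares better in the 28-day tables.

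A third reply concerns collection. Protocol 3.5.7.2 also provides for AEs before vaccination to be analysed separately from TEAEs, and rule 1.c has a pre-treatment category. An AE that ended on Day 1 could have begun before the dose. A reader might infer that the error can only remove true post-dose events, but on this text that cannot be claimed.

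Three further readings go too far:

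- *Any AE with a partial end date is lost.* A partial end date in a later month or year is after dose 1 whatever its missing part, so the AE is kept.
- *The table described as "All unsolicited TEAEs within 60 minutes after any vaccination" is depleted.* An AE without an onset day is unlikely to have a usable onset time, and assigning the dose-1 date would not place it within 60 minutes.
- *The AE drops out of every TEAE table.* Appendix D does not say that an imputed pre-dose start makes an AE non-treatment-emergent, and SAP 7.6.2 treats all collected AEs as TEAEs.

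**Conclusion.** The point holds in two limited parts. First, an AE with a partial start date matching dose 1 and a complete end date equal to the dose-1 date is dated before dose 1, unless dose 1 fell on the first of the month (or of the year, under rule 1.b). It then lies outside [1,29] and the 28-day summaries. This conflicts with collection that begins at the first dose and with the line drawn in rule 1.c. Second, for a partial end date that cannot be ordered against dose 1, the outcome is undefined rather than a certain loss.

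The effect is probably small. The documents do not say how many AEs have incomplete dates, so no expected count can be given. The 4.2 points per participant applies only where that participant has no other AE counted in the same row. The change is still worth making, because a stated rule misdates an event feeding a primary safety endpoint and is easily corrected.

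**What to change.** In Appendix D rules 1.a.i and 1.b.i, change *is after* to *is on or after*, and add that a partial end date is treated as missing unless its known part places it clearly before the dose-1 date. Both rules then draw the line where rule 1.c does.

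The cost is one sentence in the SAP and one condition in the AE derivation program, with no new data. The downside is that an AE that truly began and ended before dosing on Day 1 could be counted as post-dose. SAP 7.6.2 says such AEs are not collected. Because Protocol 3.5.7.2 mentions analysing pre-vaccine AEs separately, the SAP should state which applies.

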10.5 Appendix E: Schedule of Events

Please refer to Table 5 in Section 6.1 Appendix 1: Schedule of Events in the protocol.

10.6 Appendix F: Immunogenicity Assessments

The following laboratory assays are planned to measure the immune response to mRNA-1893 (Table 5):

- nAb against ZIKV will be measured using PRNT, MN, RVNT and possibly additional neutralization assays.
- bAb against ZIKV will be measured by ELISA.
- IgG and IgM antibodies against envelope- and NS1-based antigens will be measured by ELISA or equivalent methodology to flaviviruses

Protocol mRNA-1893-P101 Date Issued: 25May2021

• Table 5: Immunogenicity Against Zika Virus

| Material | Component | Method | Unit |
|----------|----------------------------------|---------------------|---------------------------|
| Serum | Neutralizing antibodies against | PRNT | Fold dilution (titer) |
| | ZIKV | | |
| Serum | Neutralizing antibodies against | Reporter Virus | Fold dilution (titer) |
| | ZIKV | Neutralization Test | |
| Serum | Neutralizing antibodies against | Microneutralization | Fold dilution (titer) |
| | ZIKV | Assay | |
| Serum | binding antibodies against ZIKV | ELISA | Fold rise (concentration) |
| Serum | IgG and IgM antibodies against | ELISA | Fold rise (concentration) |
| | envelope- and NS1-based antigens | | |

Abbreviations: ELISA, enzyme-linked immunosorbent assay; PRNT, Plaque Reduction Neutralization Test.

PPD Biostatistics and Programming

Statistical Analysis Plan (SAP) Client Approval Form

| Client: | ModernaTX, Inc. |
|--|--|
| Protocol Number: | mRNA-1893-P101 |
| | |
| Document Description: | Final Statistical Analysis Plan |
| SAP Title: | A PHASE 1, RANDOMIZED, OBSERVER-BLIND, PLACEBO- CONTROLLED, DOSE-RANGING STUDY TO EVALUATE THE SAFETY, TOLERABILITY, AND IMMUNOGENICITY OF ZIKA VACCINE mRNA-1893 IN HEALTHY FLAVIVIRUS SEROPOSITIVE AND SERONEGATIVE ADULTS |
| SAP Version Number: | 3.0 |
| Effective Date: | 25MAY2021 |
| | |
| Author(s): | |
| For PPD: PPD | |
| | |
| | |
| Approved by: | |
| PPD | |
| PPD ModernaTX, Inc. Date (DD-MMM-YYYY) | |
| PPD | |
| PPD ModernaTX, Inc. Date (DD-MMM-YYYY) | |

PPD CONFIDENTIAL AND PROPRIETARY

SOP-BST-05ar06

Effective Date: 19 September 2019

Page 1 of 1
